4. ESTIMATED DURATION OF THE STUDY

Each participant will be on PrEP with medication adherence support for 48 weeks after enrollment with a post-study follow-up at 60 weeks. The primary endpoint will be measured at 48 weeks. This will be a 4-year study.

Participants taking part in the extension will continue to receive PrEP at Week 48 and every 12 weeks thereafter up to 24 weeks until approval of CCTG 605 (HRPP# 191001) or FDA approval of emtricitabine/tenofovir alafenamide (F/TAF) for use as PrEP.

5. LAY LANGUAGE SUMMARY OR SYNOPSIS (no more than one paragraph)

The purpose of this study is to evaluate and compare adherence to Pre-Exposure Prophylaxis (PrEP) in transgender-identifying or gender non-conforming individuals who receive daily, text message-based medication adherence reminders (iTAB) with vs. without brief Motivational Interviewing. This study will enroll 300 individuals (up to 100 at UCSD) to take PrEP for 48 weeks.

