Hypothesis: Among transgender MAAB persons on csHT who report perfect adherence by iTAB in the past 34 days (ie, two intracellular half-lives) the mean intracellular tenofovir-diphosphate (TFV-DP) concentrations, as measured in DBS, will be equivalent to the levels of perfect adherence previously defined in MSM.

Sub-study I Secondary Objectives

- 1. To determine whether csHT interacts with PrEP in MAAB persons that would affect hormone effectiveness, measured by estrogen concentrations assessed at Weeks 0 and 12 of study follow-up.
 - **Hypothesis**: Among transgender MAAB persons on csHT, estrogen concentrations will not change significantly between baseline (Week 0) and Week 12 in individuals taking PrEP and receiving stable estrogen therapy (controlling for route and formulation).
- 2. To determine TFV-DP in MAAB of all adherence levels compared to not taking csHT, adjusting for confounding factors.
- 3. To determine TFV-DP in MAAB taking versus not taking antiandrogen medications (i.e., spironolactone, finasteride)
- 4. To measure the change in testosterone concentrations between baseline and Week 12 in female-assigned at birth (FAAB) taking PrEP and receiving stable testosterone therapy.
- 5. To determine emtricitabine-triphosphate (FTC-TP) concentrations (a measure of recent adherence) in TG / GNC persons of all adherence levels taking versus not taking hormones.
- 6. To determine changes in desired effects of csHT in TG / GNC persons taking PrEP as measured by the Body Image Scale (BIS).

Sub-study IV Objectives:

- 1. To determine the impact of genital STIs on CVF TFV levels.
- 2. To determine the impact of cytokine mediators of CV inflammation on CVF TFV levels.
- 3. To determine the impact of CV microbiome on CVF TFV levels.

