¹ Only for participants curre	ently taking	n PrFP Pai	rticinants red	uirina PrFI	P dispensation dur	ing an Interi	m visit v	vill rece	ive enou	ah PrFP

Only for participants currently taking PrEP. Participants requiring PrEP dispensation during an Interim visit will receive enough PrEP to last until the next regular study visit.

Adherence and Behavioral Assessments

We will measure adherence using the self-report daily text messages. These texts will include a personalized lead-in reminder message (e.g., "Those who are closest to you care about your health") and participants will be asked "Did you take your dose today? Reply: Y) Yes N) No P) Postpone". If 'Postpone' is selected, participants will receive a follow-up message 1 hour later asking them if they took their medication (Yes or No). Participants will also have the option of determining the word used to describe the study drug (e.g., 'med', 'dose', or other personal choice). Nonresponse or a 'No' response will be counted as not taking their dose. At each follow-up

² Participants with medication interruption greater than 14 days will require confirmation of HIV seronegative status prior to re-initiation of PrEP. Re-initiation must be achieved prior to the end of the week 36 visit.

³ Only for participants capable of becoming pregnant

⁴ Only for participants currently taking csHT. Baseline and Week 12 only.

⁵ STI screen only at week 24

⁶ Week 0 DBS collected only if participant is already taking PrEP at Baseline

⁷ Interim visit for: HIV testing if off PrEP for over 1 week and had high risk event, consider NAT or Ab/Ag; STI testing only if has symptoms (urethral discharge, genital sore); if seroconverted outside study; adverse event assessment

[†] UCSD-only sub-study evaluation. Additional specimens will be collected from anatomic site of positive GC at time of treatment. ♦ UCSD-only study extension

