visit, the ACTG four-day questionnaire will be administered using the web-based data capture system. The instrument tracks the number of doses skipped over the past four days and reasons why medications may have been skipped. In addition, we will ask their ability to adhere by Likert scale and use the Visual Analog Scale (VAS), which appears as an ordinal scale representing the percent of medication taken relative to that which has been prescribed over the past 4 weeks. Subjects are presented with a line anchored at 0% and 100% and are asked to mark a line on the scale indicating their own PrEP adherence [26]. Finally, we will administer other self-report questions that have been shown to get people off of the ceiling as it relates to self-reported adherence.

In the standard study visit, the coordinator will perform HIV testing and blood work, review test results, provide TDF/FTC prescriptions, discuss medication use, adherence, risk reduction and troubleshoot any barriers. The standard behavioral survey will include assessment of TDF/FTC adherence, HIV transmission risk behaviors, substance use, depression scores and other risk behavior details (e.g., sexual partnerships, sexual acts, condom use).

Regimens, Administration, and Dosing

Emtricitabine/tenofovir disoproxil fumarate fixed-dose combination containing 200 mg of emtricitabine and 300 mg tenofovir disoproxil fumarate will be administered orally as one tablet once daily with or without food.

Enough study product should be dispensed to last until the subject's next in-person scheduled visit.

Subjects will be randomized 1:1 to one of the two treatment arms:

ARM A: FTC/TDF 200/300 mg once daily + iTAB

ARM B: FTC/TDF 200/300 mg once daily + iTAB + MI-B

Participants will participate in this study until 48 weeks. Subjects will receive study treatment for the duration of the study unless they meet criteria for discontinuation.

Personal Health Information Data Collection

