Descriptive analysis will be performed for all the secondary outcomes. For comparisons between the two study arms, Fisher's exact test will be used for categorical outcomes; t-test or Wilcoxon rank sum test will be used for continuous outcomes. Multivariable logistic regression model will be used to study factors associated with poor adherence. Factors will include demographics, substance use, untreated mental illness, socieconomic status, low health/HIV and system literacy, fear of disclosure and non-English language. To evaluate changes in risk behavior after initiation of PrEP, descriptive summary will be provided for the number of HIV positive/unknown status partners and any unprotected anal intercourse with an HIV positive/unknown status partner by visit (at w12, 24, 36 and 48). Wilcoxon signed rank test will be used for comparison at each follow-up visit to the baseline visit. GEE model will be used to assess the change in risk behavior over time.

Safety analysis

Safety data will be reported for all the randomized subjects while they were taking or immediately (30 days) after taking study drug (as treated analysis). Tables will summarize the number of serious adverse events, adverse events (grade 2 or higher), PrEP discontinuation due to adverse events, by study arms and overall. Fisher's exact test will be used to compare the rates between the two groups. The time to TDF/FTC discontinuation due to adverse events will be compared between groups using the log-rank test and plotted using Kaplan-Meier curves.

SUB-STUDY I DESIGN

This pharmacologic sub-study will use the main study cohort to determine the interaction of cross-sex hormone therapy (csHT) on PrEP efficacy as measured by TFV-DP and FTC-TP DBS intracellular levels, and of PrEP on csHT effectiveness as measured by quantitative hormone levels in plasma.

SUB-STUDY I PROCEDURES

Subjects will be consented for participation in the sub-study at the main study's Screening Visit.

As part of the main study, plasma and DBS samples will be collected at Baseline and every 12 weeks. A Baseline DBS sample will be collected only if the subject is already on PrEP at the time of Baseline. Detailed concomitant hormone use, including route and frequency, will be collected at every clinic visit. Daily iTab responses will be used as a self-reported adherence measure.

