The primary outcome is the intracellular TFV-DP levels, as measured in DBS, which is a continuous variable. Comparison between the MAAB and the existing MSM data that will be compared using a two-sample t-test. Differences in the means between the two groups, along with the standard deviations (SD) and their 95% confidence intervals will be reported. As a secondary/sensitivity analysis, multiple regression analysis will be performed to study the association between clinical and demographic factors (age, race, ethnicity, education, socioeconomic status, sexual risk behaviors, substance use, depression, concomitant medications) and group, adjusting for baseline demographic, stratification variables, and clinical characteristics. Variables significantly associated with both group and outcome (p<0.10) will be included in a multiple regression model as covariates.

For the main secondary hypothesis, in MAAB on csHT, to determine the change between baseline and week 12 estradiol levels in individuals taking PrEP and receiving stable estrogen replacement (controlling for route, dose and formulation), we will use a paired t-test. As estradiol concentrations can be unpredictable, we will measure estradiol concentrations in individuals choosing not to initiate PrEP at the same time points. Similar to 3A, multiple regression models will be developed if there are factors that require adjustment in this model.

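### The non-initiator group meant to guard the estradiol analysis has no place in the trial, leaving an uncontrolled week 0 to week 12 comparison

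*Combined protocol and SAP*

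**What the plan says.** The first secondary objective of sub-study I (Section 6) predicts that "estrogen concentrations will not change significantly between baseline (Week 0) and Week 12 in individuals taking PrEP", in people on stable estrogen. No equivalence margin is attached. For this hypothesis the sub-study Analysis Plan (Section 9) says "we will use a paired t-test", controlling for route, dose and formulation. It then gives a caution, "As estradiol concentrations can be unpredictable", and answers it: "we will measure estradiol concentrations in individuals choosing not to initiate PrEP at the same time points". It names no test comparing those people with PrEP takers. Regression adjustment is mentioned only as a possibility.

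On who is available, the Sub-study I Design says "This pharmacologic sub-study will use the main study cohort". Section 4 says of that cohort: "Each participant will be on PrEP with medication adherence support for 48 weeks after enrollment". The control arm also receives the drug: "ARM A: FTC/TDF 200/300 mg once daily + iTAB". Arm B is the same with brief motivational interviewing added. Footnote 4 to the Schedule of Evaluations sets hormone sampling: "Only for participants currently taking csHT. Baseline and Week 12 only".

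**The concern.** The plan recognises that estradiol can move for reasons other than PrEP, and a concurrent PrEP-free group is the safeguard it offers. If that group cannot be formed, the week 0 to week 12 change in PrEP takers has nothing to be set against. A common shift over those 12 weeks, for example in how regularly hormones are taken or in how long after the last hormone dose blood is drawn, would be indistinguishable from an effect of PrEP.

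The error can run either way. Drift may produce a significant change that is read as an interaction. It may also offset a real effect and give the non-significant result that the hypothesis predicts, which would be read as reassurance. Section 7 says that fear of weaker hormone therapy may keep transgender women from wanting PrEP, so either misreading could affect uptake.

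**Working it through.** **Step 1. Look for the group in the documents.**

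- Source: sub-study I draws on the main cohort (Sub-study I Design).
- Exposure: Section 5 describes 300 people enrolled to take PrEP, both arms receive FTC/TDF (Regimens, Administration, and Dosing), and a qualifying participant has 30 days to complete baseline and start PrEP (Screening Visit).
- Projected numbers: Sample Size and Power expects 280 of 300 to be assigned male at birth (MAAB), split into 196 on feminizing hormones (280 × 0.70) and 84 on none. The text mentions no PrEP-free group; the accompanying Figure 2 is not shown.
- Nearest alternative: participants who stop drug but stay on study keep the visit schedule, and hormone sampling is not among the listed exceptions. They have already initiated, so they are not the group named.
- Another subgroup: exclusion criterion 5 lets people already on TDF/FTC switch to study drug. Their week 0 sample is taken on PrEP, so their change does not measure initiation.

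No eligibility route, schedule, number or between-group comparison for non-initiators was found.

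**Step 2. Is there a figure to reproduce?** There is none for estradiol: no SD, effect size, margin or power. The sub-study's stated sample size of 45 belongs to the TFV-DP aim. It does reproduce: [350 × (1.645 + 0.842) / (230 − 100)]² = 44.8, rounded up to 45. It has no bearing here.

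**Step 3. Illustrate what drift does to the paired test.** Assume no PrEP effect and a systematic drift of d, in SDs of the within-person change. The two-sided 5% paired t-test has noncentrality d√n. For n = 196 and d = 0.2 this is 0.2 × 14 = 2.8, against a critical value of about 1.97. Probability of p<0.05 from the noncentral t:

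| Assumed drift (SD of change) | 196 pairs | 100 pairs |
|---|---|---|
| 0 | 0.05 | 0.05 |
| 0.1 | 0.29 | 0.17 |
| 0.2 | 0.80 | 0.51 |
| 0.3 | 0.99 | 0.84 |

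The 196 treats every predicted hormone user as analysable. The 100 is an assumed smaller number, because sub-study consent, the stable-regimen requirement and week 12 attendance all reduce it.

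**Step 4. What a real comparison group would need.** With 196 PrEP takers, m non-initiators and equal SDs of change, the difference in change detectable with 80% power is (1.960 + 0.842) × √(1/196 + 1/m). That is 0.91 SD for m = 10, 0.66 for m = 20, 0.44 for m = 50 and 0.34 for m = 100. With m = 0 the difference cannot be estimated. A handful of incidental non-starters would not supply the safeguard.

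**The case against.** The strongest reply is that the test does not need the group. The hypothesis is a within-person change, the paired t-test matches it, and the non-initiator sentence is an addition with no analysis attached. This stands in part: it would be too strong to infer that the formal test depends on non-initiators. But without them the plan has no answer to its own caution about estradiol.

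A reader might also infer that the group is certain to be empty. The documents do not establish that. The modified intent-to-treat definition, limited to randomized participants dispensed PrEP at baseline, leaves room for some who were not dispensed drug. Footnote 4 ties hormone sampling to hormone use and not to PrEP. The text also refers to a fuller protocol, a procedures manual and a later SAP that takes precedence. What can be said is that these documents provide no means of forming or using the group.

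The reply is right on mechanism too. Undirected variability widens the SD of the change without biasing its mean; only a systematic shift does that, and the documents do not show that one exists. Regression to the mean is not a ready explanation, since nobody is selected on estradiol. The stable-estrogen restriction and the control for route, dose and formulation limit drift from regimen changes. They do not deal with the timing of sampling after a hormone dose, or with a common shift in assay or hormone-taking habits.

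Finally, this is a secondary objective of a sub-study, and the Analysis Plan itself ranks hormone levels below satisfaction with physical traits. That limits the weight of the point but does not remove it.

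**Conclusion.** The point holds in limited form. The plan promises a concurrent comparison that the described trial has no means to deliver, so the estradiol test is an uncontrolled before-after comparison. It can show whether estradiol changed in PrEP takers, but not whether PrEP was the reason. The primary endpoint is unaffected.

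The 80% and 51% show sensitivity to an assumed drift of 0.2 SD. A reader might take them as the trial's expected false-positive rate; the documents give no SD or drift to support that.

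Nor do the documents support replacing the paired test with a regression on TFV-DP as the sole basis for a PrEP claim. Sub-study I asks whether hormones alter TFV-DP, and Section 7 calls the concern bidirectional, so the exposure may itself depend on hormones. Section 6 equates 34 days with two half-lives, about 17 days each, so someone who stopped 17 days earlier would still hold about half the level. DBS is not collected off drug, so entering zero for people who stopped would be invented data.

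**What to change.** In the sub-study I Analysis Plan:

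- Delete the sentence on people who do not initiate PrEP.
- Keep the paired change with its 95% confidence interval, reported as a within-person change and not as an effect of PrEP.
- Restrict it to participants not on PrEP at baseline. Show those already on PrEP separately, as an internal indication of drift without initiation. They are identifiable, because baseline DBS is collected only from them.
- Record time since the last hormone dose at weeks 0 and 12, and adjust for it together with route, dose and formulation.
- Add, as a supportive observational analysis only, the association of estradiol change with week 12 TFV-DP among those with a measured level. Impute no zero for participants who stopped. State that adherence may confound it and that hormones may affect TFV-DP.
- Apply the same to testosterone in participants assigned female at birth. The plan expects only about 20 participants outside the MAAB group (300 − 280), so adjusted results there will be thin.

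The cost is one added question at two existing visits, analysis wording, and a more limited causal claim. The restriction also loses some precision: the change detectable with 80% power is (1.960 + 0.842)/√n, or 0.20 SD with 196 pairs and 0.28 SD with 100. The documents do not say how many participants will already be on PrEP at baseline.

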At Weeks 0, 12, and 48, applicable subjects will complete the Body Image Scale (mBIS) questionnaire, and answer questions about general hormone therapy satisfaction.

SUB-STUDY STATISTICAL CONSIDERATIONS

Sample Size and Power

The primary aim of this analysis is to determine if PrEP interacts with hormone therapy in either direction that would impact either i) efficacy of PrEP to reduce HIV acquisition or ii) hormones to achieve desirable gender traits. Of our 300 person cohort, we estimate that 280 individuals will be MAAB Of those 280 MAAB, we predict that 70% will be taking feminizing hormones (n=196) and 30% will be on no hormonal therapy (n=84), based on previous population estimates (97). Based on adherence results in individuals randomized to iTAB (98), we estimate that 25% of participants will have perfect adherence to PrEP.

[figure not shown]

Figure 2: Predicted Numbers of Individuals on HRT and PrEP

Statistical power is based on a one-sample non-inferiority test to see if the TFV-DP concentration of perfectly adhered MAAB persons is equivalent to MSMs on average under an acceptable margin. The following assumptions are made: i) Using PK modeling of HIV-uninfected men and women, it has been shown that perfect adherers (i.e. daily dosing for 7 days) have TFV-DP concentrations of 1560 (IQR 1246-2029) fmol/punch as determined in MSM; ii) Since this is a non-inferiority study, we will assume the expected sample mean for MAAB is around 1560 fmol/punch, or slightly lower. In other words, we will assume the mean difference in TFV-DP concentrations between MAAB and MSMs is approximately 0 (ranges from -180 to 50); and iii) We believe that a difference of less than 230 fmol/punch (equivalent to 1 tablet per week dosing) in the TFV-DP concentration can be considered non-inferiority which will be the lower limit of acceptable variation. Thus, we will set the non-inferiority margin to be 230.

Assuming the standard deviation is 350, if the true mean TFV-DP concentration for MAAB is 1360 fmol/punch (ie, 100 fmol/punch lower than MSMs), then 45 subjects are required to be 80% confident that the lower limit of a one-sided 95% confidence interval of the mean difference between MAAB and MSMs will be above the non-inferiority limit of -230.

Analysis Plan

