Other secondary analyses will explore further interactions between PrEP and csHT in MAAB we will perform analyses of the following potential interactions: a) TFV-DP in transgender persons (MAAB and FAAB) of all adherence levels compared to not taking csHT, b) TFV-DP in MAAB taking versus not taking antiandrogen medications (i.e. spironolactone and finasteride) and c) emtricitabine-triphosphate (FTC-TP) concentrations (recent adherence measure) in transgender persons of all adherence levels taking versus not taking hormones. These analyses will be analogous to the descriptive analyses in the primary outcomes. For FAAB transgender individuals, to determine the change between baseline and week 12 testosterone levels in individuals taking PrEP and receiving stable testosterone replacement (controlling for route, dose and formulation), we will use a paired test. For hormone therapy satisfaction, the main outcome of interest to these individuals is maintaining the physically desirable characteristics that the csHT provide. Thus, it is not the hormone levels that are as important

as the satisfaction with these traits. For the entire cohort of MAAB who are on stable csHT dosing (as defined as no change from baseline to week 12) from baseline to week 12 and from baseline to week 48 we will compare the hormone satisfaction with physical traits ranked for satisfaction using the BIS and summed for overall satisfaction score to compare between weeks 0, 12 and 48. Similarly, we will use the BIS for FAAB on stable csHT assessing physical traits compared at weeks 0, 12 and 48.

SUB-STUDY IV PROCEDURES

At Baseline, eligible participants will consent for additional sub-study sample collection on the main study informed consent form. Genital collection for *Neisseria gonorrhoeae* and *C. trachomatis* will be done at Baseline and Week 24 as part of the main study STI screening procedures.

For the sub-study, two genital swabs for microbiome and cytokine testing will be collected at Baseline and Week 24. Additional genital swabs for a vaginitis multiplex assay, herpesvirus and HPV testing as well as CVF collection via aspirator for TFV levels will be collected at Week 24.

Sub-study IV	Study Weeks of Follow-up					
Schedule of Evaluations	Screen	Wk 0	Wk 24			
Window	14 days	30 days	+/- 4 weeks			
Informed Consent	Х					
CV swab for cytokine testing		Х	Х			
CV Swab for microbiome		Х	X			
CVF collection for drug concentration TFV			X			

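### Sub-study I's antiandrogen comparison does not condition on estrogen, so part of any estrogen effect on TFV-DP could appear as an antiandrogen effect; its pooled csHT comparison does not match objective 2

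*Combined protocol and SAP*

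**What the plan says.** The relevant text is in section 9, Sub-study Statistical Considerations (Sample Size and Power; Analysis Plan), and in section 6, Sub-study I Secondary Objectives.

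- **Comparison (b).** The Analysis Plan lists "TFV-DP in MAAB taking versus not taking antiandrogen medications (i.e. spironolactone and finasteride". Objective 3 has the same content: "To determine TFV-DP in MAAB taking versus not taking antiandrogen medications (i.e., spironolactone, finasteride". Neither mentions estrogen.
- **Method for (a) to (c).** "These analyses will be analogous to the descriptive analyses in the primary outcomes". The primary comparison is described as "Comparison between the MAAB and the existing MSM data that will be compared using a two-sample t-test". A multiple regression follows as a secondary or sensitivity analysis. Its candidate covariates include concomitant medications and the stratification variables, and variables enter if associated at p<0.10 with both group and outcome.
- **Expected hormone use.** Of 280 MAAB participants, "we predict that 70% will be taking feminizing hormones (n=196) and 30% will be on no hormonal therapy (n=84".
- **Comparison (a).** The Analysis Plan gives "TFV-DP in transgender persons (MAAB and FAAB) of all adherence levels compared to not taking csHT". Objective 2 reads "To determine TFV-DP in MAAB of all adherence levels compared to not taking csHT, adjusting for confounding factors".
- **Comparison (c), FTC-TP.** The plan compares "concentrations (recent adherence measure) in transgender persons of all adherence levels taking versus not taking hormones". Objective 5 likewise covers all TG/GNC persons and states no adjustment.
- **Data available.** Under Sub-study I Procedures, hormone use with route and frequency is recorded at each clinic visit.

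**The concern.** Section 7 (Sub-study II Background) describes hormone therapy as estrogen together with antiandrogens. On that description, people on no hormonal therapy take neither drug and fall into the non-taker group of (b), while the takers come from those on feminizing therapy. The two groups then differ in estrogen exposure by construction. A simple difference in means cannot tell an antiandrogen effect from an estrogen effect, and a participant could be told that the wrong drug lowers PrEP levels.

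Comparison (a) has a different problem. The objective and the analysis plan disagree on the population and on adjustment, so objective 2 is not carried out as written. Pooling also counts estrogen and testosterone as one exposure.

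**Working it through.** **The plan's own figures.** The plan states no sample size for (a), (b) or (c). Its hormone counts reproduce: 280 × 0.70 = 196 and 280 × 0.30 = 84. The only sample size in Sub-study I, 45 for the primary non-inferiority question, also reproduces if the stated difference of 100 fmol/punch is taken at face value: (350 × (1.645 + 0.842) / (230 − 100))² = 44.8. It does not concern these comparisons.

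**Share of an estrogen effect that appears in (b).** Suppose estrogen shifts TFV-DP by D and antiandrogens do nothing. The difference between takers and non-takers is then L × D, where L is the estrogen share among takers minus the estrogen share among non-takers.

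Assumptions not in the documents: all 196 take estrogen, nobody takes an antiandrogen without estrogen, and a fraction f of the 196 take one. Takers number 196f, non-takers number 84 + 196(1 − f), and L = 84 / (84 + 196(1 − f)).

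| f | Takers | Non-takers | L | L × 230 (fmol/punch) |
|---|---|---|---|---|
| 40% | 78.4 | 201.6 | 0.42 | 96 |
| 50% | 98 | 182 | 0.46 | 106 |
| 70% | 137.2 | 142.8 | 0.59 | 135 |
| 90% | 176.4 | 103.6 | 0.81 | 186 |

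The 230 is the plan's non-inferiority margin, borrowed for scale; it is not an expected effect. The last column scales with D: at D = 100 it runs from 42 to 81.

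**Chance of a nominally significant antiandrogen result when there is none.** Take D = 230, a two-sided 0.05 test and a normal approximation, with SE = SD × √(1/takers + 1/non-takers).

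- SD 350 (planning value): at f = 50%, SE = 43.9 and 106/43.9 = 2.42, a chance of 68%. At f = 70% and 90% it is 90% and 99%.
- SD 694 (observed in perfectly adherent MSM, section 7, Preliminary Data): 23%, 37% and 58%.

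**Weaker assumptions on overlap.**

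- If 20% of the 84 (16.8 people) took an antiandrogen without estrogen, then at f = 40%, L = 78.4/95.2 − 117.6/184.8 = 0.19. At f = 90% it is 0.69.
- If, at f = 60%, 20 of the 118 takers used no estrogen, then L = 97.6/117.6 − 78.4/162.4 = 0.35. That is 80 fmol/punch at D = 230, against 0.52 and 119 with full overlap.
- If D = 0, nothing leaks at any f.

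**Pooled comparison (a).** 300 − 280 leaves about 20 FAAB participants. If 50%, 70% or 100% of them take testosterone, they make up 10/206 = 4.9%, 14/210 = 6.7% or 20/216 = 9.3% of the hormone group. At least about 90% of that group is therefore on feminizing hormones.

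**Precision of (b) restricted to estrogen users.** Detectable difference with 80% power = (1.960 + 0.842) × SD × √(1/n₁ + 1/n₂), assuming every expected participant contributes a sample.

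| f | Groups if restricted | SD 350: as planned → restricted | SD 694: as planned → restricted |
|---|---|---|---|
| 50% | 98 / 98 | 123 → 140 | 244 → 278 |
| 70% | 137 / 59 | 117 → 153 | 232 → 303 |
| 90% | 176 / 20 | 121 → 233 | 241 → 463 |

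**The case against.** The strongest reply is that the plan may already cover this. The primary-outcome paragraph includes a regression with concomitant medications and stratification variables, one of which is sex assigned at birth. Section 9 also defers detail in the main study to a later SAP. This stands only in part: the regression is a sensitivity analysis for MAAB versus MSM, the secondary analyses are tied to the descriptive ones, and the p<0.10 entry rule would not guarantee that estrogen enters.

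A second reply is that the size rests on assumptions. That stands. Co-use is not given, some of the 196 might take antiandrogens alone, and the plan itself assumes a MAAB–MSM difference near 0 (−180 to 50). The observed SD of 694 also makes a false finding less likely than the planning SD suggests.

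A third reply is that these are exploratory analyses on which no stated decision depends. That stands too, and it limits the weight of the point.

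A reader might go further than the documents allow in three ways:

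- That the pooled comparison answers neither the feminizing nor the masculinizing question. With about 20 FAAB participants, it is largely a feminizing-hormone estimate.
- That (a) and (c) also have a mixed comparator. Their comparator is hormone-free throughout and varies only by sex assigned at birth.
- That section 6 promises adjustment for FTC-TP. It promises it only in objective 2.

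**Conclusion.** The point holds as a limited one. As written, (b) is a confounded contrast, and part of any estrogen effect could be read as an antiandrogen effect. The part is about 42% to 81% if all 196 take estrogen, 40% to 90% of them also take an antiandrogen, and nobody takes one without estrogen. It falls as antiandrogen use without estrogen rises, and it needs an estrogen effect to exist. A reader might infer that the whole estrogen effect would be reported as an antiandrogen effect; the planned numbers do not support that, because some non-takers would also be on estrogen unless co-use were complete.

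For (a), the finding is a conflict between objective 2 and the Analysis Plan. Its numerical effect on the pooled estimate is small. The loss is that any testosterone effect is hidden and the MAAB-only, adjusted analysis is not carried forward. The Sub-study I primary question and its sample size are untouched.

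**What to change.** In the SAP, before database lock:

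1. Define (b) as estrogen plus antiandrogen versus estrogen alone, among MAAB estrogen users. If few take estrogen alone, pre-specify a model adjusting for estrogen use instead, and report the interval. If nobody takes an antiandrogen without estrogen, such adjustment recovers little precision, because the antiandrogen effect still rests on the small estrogen-only group.
2. Show spironolactone and finasteride separately as description only, since the documents give no counts by agent.
3. Reconcile (a) with objective 2: run it in MAAB with the stated adjustment, and name the covariates.
4. Report FAAB separately and descriptively for (a) and (c).

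The hormone data already being collected should support this, so the change is to wording. The cost is precision in (b): modest at 50% to 70% co-use, but at 90% the detectable difference roughly doubles, to 233 fmol/punch at SD 350. FAAB intervals will be wide with about 20 people.
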